7.1.1 Management of Hypertension

Hypertension is a recognized side effect of treatment with drugs inhibiting VEGF signaling. Investigators should therefore ensure that subjects enrolled to receive treatment with lenvatinib have BP of $\leq 150/90$ mm Hg at the time of study entry and, if known to be hypertensive, have been on a stable dose of antihypertensive therapy for at least 1 week before Cycle 1/Day 1. Early detection and effective management of hypertension are important to minimize the need for lenvatinib dose interruptions and reductions.

Antihypertensive agents should be started as soon as elevated BP (systolic BP ≥ 140 mm Hg or diastolic BP ≥ 90 mm Hg) is confirmed on 2 assessments a minimum of 1 hour apart. One BP assessment is defined as the mean value of 3 measurements at least 5 minutes apart. The choice of antihypertensive treatment should be individualized to the subject's clinical circumstances and follow standard medical practice. For previously normotensive subjects, appropriate antihypertensive therapy should be started when systolic BP ≥ 140 mm Hg or diastolic BP ≥ 90 mm Hg is first observed on 2 assessments a minimum of 1 hour apart. For those subjects already on antihypertensive medication, treatment modification may be necessary if hypertension persists. For subjects with hypertension and proteinuria, appropriate therapy, eg, angiotensin-converting enzyme inhibitor or angiotensin-II receptor antagonist, is preferred (Kilfoyle, et al., 2009).

Lenvatinib should be withheld in any instance where a subject is at imminent risk to develop a hypertensive crisis or has significant risk factors for severe complications of uncontrolled hypertension (eg, BP $\geq 160/100$ mm Hg, significant risk factors for cardiac disease, intracerebral hemorrhage, or other significant comorbidities). Once the subject has been on the same hypertensive medications for at least 48 hours and the BP is controlled, lenvatinib should be resumed as described below.

During the Treatment Period, subjects with systolic BP ≥ 160 mm Hg or diastolic BP ≥ 100 mm Hg must have their BP monitored on Day 15 or more frequently as clinical indicated until systolic BP has been ≤ 150 mm Hg and diastolic BP has been ≤ 95 mm Hg for 3 consecutive months. If a repeat event of systolic BP ≥ 160 mm Hg or diastolic BP ≥ 100 mm Hg occurs, the subject must resume the Day 15 evaluation until systolic BP has been ≤ 150 mm Hg and diastolic BP has been ≤ 95 mm Hg for 3 consecutive months.

The following guidelines should be followed for the management of systolic BP ≥ 160 mm Hg or diastolic BP ≥ 100 mm Hg confirmed on repeat measurements after 1 hour:

1. Continue lenvatinib and institute antihypertensive therapy for subjects not already receiving antihypertensive medication
2. For those subjects already on antihypertensive medication, dose of the current agent may be increased, if appropriate, or 1 or more agents of a different class of antihypertensive should be added.
3. If systolic BP ≥ 160 mm Hg or diastolic BP ≥ 100 mm Hg persists despite maximal antihypertensive therapy, then lenvatinib administration should be interrupted. It should be restarted at one lower dose level as specified in Table 3 only when systolic BP ≤ 150 mm Hg and diastolic BP ≤ 95 mm Hg and the subject has been on a stable dose of antihypertensive medication for at least 48 hours
 - If systolic BP ≥ 160 mmHg or diastolic BP ≥ 100 mmHg recurs on the first dose reduction despite optimal management of hypertension with antihypertensive medications (either by dose increase or the addition of a different class of restarted at an additional dose reduction as specified in Table 3 only when systolic BP ≤ 150 mmHg and diastolic BP ≤ 95 mmHg and the subject has been on a stable dose of antihypertensive medication for at least 48 hours.
 - If systolic BP ≥ 160 mmHg or diastolic BP ≥ 100 mmHg recurs on the second dose reduction despite optimal management of hypertension with antihypertensive medications (either by dose increase or the addition of a different class of antihypertensive), then lenvatinib administration should be interrupted. It should be restarted at a third dose reduction as specified in Table 3 only when systolic BP ≤ 150 mmHg and diastolic BP ≤ 95 mmHg

and the subject has been on a stable dose of antihypertensive medication for at least 48 hours.

The following guidelines should be followed for the management of Grade 4 hypertension (life-threatening consequences):

- Institute appropriate medical management
- Discontinue study drug

7.1.2 Management of Proteinuria

Regular assessment of proteinuria should be conducted as detailed in the study calendar. Guidelines for assessment and management of proteinuria:

1. Grading will be based on the 24-hour urinary protein result. Management of lenvatinib administration will be based on the grade of proteinuria according to instructions contained the table above, “Dose Modifications for Lenvatinib Treatment-Related Toxicity.”
2. A 24-hour urine collection (within 72 hours) to verify the grade of proteinuria for protein quantitation is required in the following situations:
 - a. The first (initial) occurrence of $\geq 2+$ proteinuria on urine dipstick while on study drug
 - b. A subsequent increase in severity of urine dipstick proteinuria occurring on the same lenvatinib dose level
 - c. When there has been a lenvatinib dose reduction and at the new dose level the urine protein dipstick result is 2+, 3+, or 4+
3. Urine dipstick testing for subjects with proteinuria $\geq 2+$ should be performed on Day 15 (or more frequently as clinically indicated) until the results have been 1+ or negative for 3 consecutive months.

Grading of proteinuria should be performed according to CTCAE v 5 but will be based on the 24-hour urine collection for total protein result, if a 24-hour urine was performed at that time point.

For subjects with lenvatinib-related toxicity, the dose reduction and/or interruption instructions provided in the table above, “Dose Modifications for Lenvatinib Treatment-Related Toxicity,” should be followed.

7.1.3 Management of Hepatotoxicity

Regular monitoring of liver function tests (eg, alanine transaminase [ALT], aspartate transaminase [AST], bilirubin levels) should be conducted as detailed in the study calendar and as clinically indicated. If signs occur indicating a decrease in liver function by 1 grade or more from baseline, the instructions contained in the table above, “Dose Modifications for Lenvatinib Treatment-Related Toxicity,” should be followed. Appropriate supportive care should be provided together with close monitoring. If hepatic failure occurs the study drug must be discontinued.

7.1.4 Management of Thromboembolic Events

Subjects should be advised to pay attention to the symptoms suggestive of venous thromboembolic events, which include acute onset of dyspnea, chest pain, cough, hemoptysis, tachypnea, tachycardia, cyanosis, DVT signs including lower-extremity swelling, redness and warmth to touch or tenderness. In case any of these signs or symptoms appear, subjects should be instructed to report such signs and symptoms promptly to the treating physician. If a thromboembolic event is confirmed, instructions contained in the table above, “Dose Modifications for Lenvatinib Treatment-Related Toxicity,” should be followed. Appropriate supportive care should be provided together with close monitoring. If a subject experiences life-threatening (Grade 4) thromboembolic reactions, including pulmonary embolism, the study drug must be discontinued.

7.1.5 Management of Posterior Reversible Encephalopathy Syndrome (PRES)

In clinical studies with lenvatinib, events of posterior reversible encephalopathy syndrome (PRES) were reported in less than 1% of lenvatinib-treated subjects. PRES is a neurological disorder that can present with headache, seizure, lethargy, confusion, altered mental function, blindness, and other visual or neurological disturbances. Mild to severe hypertension may be present. MRI is necessary to confirm the diagnosis of PRES. Appropriate measures should be taken to control blood pressure. In subjects with signs or symptoms of PRES, dose interruptions, reductions, or discontinuation may be required per instructions included in the table above, “Dose Modifications for Lenvatinib Treatment-Related Toxicity.” Please refer to Section 7 of the Investigator’s Brochure for further information on lenvatinib, including the full set of special warnings and precautions for use (Section 7.4.4).

7.1.6 Management of Hypocalcemia

Serum calcium should be monitored every 3 weeks per the study calendar. Hypocalcemia should be treated per institutional guidelines (e.g., using, as appropriate, calcium, magnesium, and Vitamin D supplementation) until resolution.

7.2 Pembrolizumab

Pembrolizumab dose interruption for subjects who experience pembrolizumab-related toxicity will be in accordance with the table below. Adverse events (both nonserious and serious) associated with pembrolizumab exposure, including coadministration with additional compounds, may represent an immunologic etiology. These AEs may occur shortly after the first dose or several months after the last dose of treatment. Pembrolizumab must be withheld for drug-related toxicities and severe or life-threatening AEs as per the table below.

Dose Modification and Toxicity Management Guidelines for Immune-related Adverse Events Associated with Pembrolizumab and Combination Therapy

General instructions: 
 1. Corticosteroid taper should be initiated upon AE improving to Grade 0 or 1 and continue to taper over at least 4 weeks. 2. For situations where pembrolizumab has been withheld, pembrolizumab can be resumed after AE has improved to Grade 0 or 1 and corticosteroid has been tapered. Pembrolizumab should be permanently discontinued if AE does not resolve within 12 weeks of last dose or corticosteroids cannot be reduced to ≤ 10 mg prednisone or equivalent per day within 12 weeks. 				
*For severe and life-threatening irAEs, IV corticosteroid should be initiated first followed by oral steroid. Other immunosuppressive treatment should be initiated if irAEs cannot be controlled by corticosteroids.				
Immune-related Adverse Event	Toxicity Grade or Conditions (CTCAE V5.0)	Action Taken with Pembrolizumab	irAE Management with Corticosteroids and Other Therapies	Monitor and Follow-up
Pneumonitis	Grade 2	Withhold	Administer corticosteroids (initial dose of 1-2 mg/kg prednisone or equivalent) followed by taper. Add prophylactic antibiotics for opportunistic infections.	Monitor subjects for signs and symptoms of pneumonitis. Evaluate subjects with suspected pneumonitis with radiographic imaging and initiate corticosteroid treatment.
	Grade 3 or 4, or recurrent Grade 2	Permanently discontinue		
Diarrhea / Colitis	Grade 2 or 3	Withhold	Administer corticosteroids (initial dose of 1-2 mg/kg prednisone or equivalent) followed by taper. Subjects with diarrhea/ colitis should be advised to drink liberal quantities of clear fluids. If sufficient oral fluid intake is not feasible, fluid and electrolytes should be substituted via IV infusion.	Monitor subjects for signs and symptoms of enterocolitis (i.e., diarrhea, abdominal pain, blood or mucus in stool with or without fever) and of bowel perforation (i.e., peritoneal signs and ileus). Subjects with Grade ≥ 2 diarrhea suspecting colitis should consider GI consultation and performing endoscopy to rule out colitis
	Grade 4 or recurrent Grade 3	Permanently discontinue		
AST / ALT elevation or Increased bilirubin	Grade 2 ^a	Withhold	Administer corticosteroids (initial dose of 0.5 - 1 mg/kg prednisone or equivalent) followed by taper.	Monitor with liver function tests (consider weekly or more frequently until liver enzyme value returned to baseline or is stable)
	Grade 3 ^b or 4 ^c	Permanently discontinue	Administer corticosteroids (initial dose of 1-2 mg/kg prednisone or equivalent) followed by taper.	

Type 1 diabetes mellitus (T1DM) or Hyperglycemia	Newly onset T1DM or Grade 3 or 4 hyperglycemia associated with evidence of β -cell failure	Withhold ^d	Initiate insulin replacement therapy for subjects with T1DM. Administer antihyperglycemic in subjects with hyperglycemia.	Monitor subjects for hyperglycemia or other signs and symptoms of diabetes.
Hypophysitis	Grade 2	Withhold	Administer corticosteroids and initiate hormonal replacements as clinically indicated.	Monitor for signs and symptoms of hypophysitis (including hypopituitarism and adrenal insufficiency).
	Grade 3 or 4	Withhold or permanently discontinue ^d		
Hyperthyroidism	Grade 2	Continue	Treat with nonselective beta-blockers (eg, propranolol) or thionamides as appropriate.	Monitor for signs and symptoms of thyroid disorders.
	Grade 3 or 4	Withhold or permanently discontinue ^d		
Hypothyroidism	Grade 2-4	Continue	Initiate thyroid replacement hormones (eg, levothyroxine or liothyroinine) per standard of care.	Monitor for signs and symptoms of thyroid disorders.
Nephritis: grading according to increased creatinine or acute kidney injury	Grade 2	Withhold	Administer corticosteroids (prednisone 1-2 mg/kg or equivalent) followed by taper.	Monitor changes of renal function.
	Grade 3 or 4	Permanently discontinue		
Neurological Toxicities	Grade 2	Withhold	Based on severity of AE administer corticosteroids	Ensure adequate evaluation to confirm etiology and/or exclude other causes
	Grade 3 or 4	Permanently discontinue		
Myocarditis	Grade 1	Withhold	Based on severity of AE administer corticosteroids.	Ensure adequate evaluation to confirm etiology and/or exclude other causes
	Grade 2, 3 or 4	Permanently discontinue		

Exfoliative Dermatologic Conditions	Suspected SJS, TEN, or DRESS	Withhold	Based on severity of AE administer corticosteroids	Ensure adequate evaluation to confirm etiology or exclude other causes
	Confirmed SJS, TEN, or DRESS	Permanently discontinue		
All other irAEs	Persistent Grade 2	Withhold	Based on type and severity of AE administer corticosteroids.	Ensure adequate evaluation to confirm etiology and/or exclude other causes.
	Grade 3	Withhold or discontinue based on the type of event ^e		
	Grade 4 or recurrent Grade 3	Permanently discontinue		

AE(s)=adverse event(s); ALT= alanine aminotransferase; AST=aspartate aminotransferase; CTCAE=Common Terminology Criteria for Adverse Events; DRESS=Drug Rash with Eosinophilia and Systemic Symptom; GI=gastrointestinal; IO=immuno-oncology; ir=immune related; IV=intravenous; SJS=Stevens-Johnson Syndrome; T1DM=type 1 diabetes mellitus; TEN=Toxic Epidermal Necrolysis; ULN=upper limit of normal.

Note: Non-irAE will be managed as appropriate, following clinical practice recommendations.

a AST/ALT: >3.0 to 5.0 x ULN if baseline normal; >3.0 to 5.0 x baseline, if baseline abnormal; bilirubin:>1.5 to 3.0 x ULN if baseline normal; >1.5 to 3.0 x baseline if baseline abnormal

b AST/ALT: >5.0 to 20.0 x ULN, if baseline normal; >5.0 to 20.0 x baseline, if baseline abnormal; bilirubin:>3.0 to 10.0 x ULN if baseline normal; >3.0 to 10.0 x baseline if baseline abnormal

c AST/ALT: >20.0 x ULN, if baseline normal; >20.0 x baseline, if baseline abnormal; bilirubin: >10.0 x ULN if baseline normal; >10.0 x baseline if baseline abnormal

d The decision to withhold or permanently discontinue pembrolizumab is at the discretion of the investigator or treating physician. If control achieved or ≤ Grade 2, pembrolizumab may be resumed.

e Events that require discontinuation include but are not limited to: encephalitis, and other clinically important irAEs (eg, vasculitis and sclerosing cholangitis)

Dosing interruptions are permitted in the case of medical / surgical events or logistical reasons not related to study therapy (eg, elective surgery, unrelated medical events, subject vacation, and/or holidays). Subjects should be placed back on study treatment within 3 weeks of the scheduled interruption, unless otherwise discussed with the Sponsor. The reason for interruption should be documented in the subject's study record.

7.2.1 Supportive Care Guidelines for Infusion Reactions

Pembrolizumab may cause severe or life-threatening reactions including severe hypersensitivity or anaphylaxis. Signs and symptoms usually develop during or shortly after drug infusion and generally resolve completely within 24 hours of completion of infusion. Dose modification and toxicity management guidelines on pembrolizumab associated infusion reaction are provided in the table below.

NCI CTCAE Grade	Treatment	Premedication at subsequent dosing
Grade 1 Mild reaction; infusion interruption not indicated; intervention not indicated	Increase monitoring of vital signs as medically indicated until the subject is deemed medically stable in the opinion of the investigator.	None
Grade 2 Requires infusion interruption but responds promptly to symptomatic treatment (e.g., antihistamines, NSAIDS, narcotics, IV fluids); prophylactic medications indicated for <=24 hrs	
Stop Infusion
 
Additional appropriate medical therapy may include but is not limited to: IV fluids, antihistamines, NSAIDS, acetaminophen, narcotics
 
Increase monitoring of vital signs as medically indicated until the subject is deemed medically stable in the opinion of the investigator.
 
If symptoms resolve within one hour of stopping drug infusion, the infusion may be restarted at 50% of the original infusion rate (e.g. from 100 mL/hr to 50 mL/hr). Otherwise dosing will be held until symptoms resolve and the subject should be premedicated for the next scheduled dose.
 
Subjects who develop Grade 2 toxicity despite adequate premedication should be permanently discontinued from further trial treatment administration.
	Subject may be premedicated 1.5h (\pm 30 minutes) prior to infusion with: Diphenhydramine 50 mg po (or equivalent dose of antihistamine). Acetaminophen 500-1000 mg po (or equivalent dose of analgesic).
Grades 3 or 4 Grade 3: Prolonged (i.e., not rapidly responsive to symptomatic medication and/or brief interruption of infusion); recurrence of symptoms following initial improvement; hospitalization indicated for other clinical sequelae (e.g., renal impairment, pulmonary infiltrates) Grade 4: Life-threatening; pressor or ventilatory support indicated	
Stop Infusion.
 
Additional appropriate medical therapy may include but is not limited to: epinephrine**, IV fluids, antihistamines, NSAIDS, acetaminophen, narcotics, oxygen, pressors, corticosteroids.
 
Increase monitoring of vital signs as medically indicated until the subject is deemed medically stable in the opinion of the investigator.
 
Hospitalization may be indicated.
 
** In cases of anaphylaxis, epinephrine should be used immediately.
 
Subject is permanently discontinued from further trial treatment administration.
	No subsequent dosing
Appropriate resuscitation equipment should be available in the room and a physician readily available during the period of drug administration.		

For further information, please refer to the Common Terminology Criteria for Adverse Events v5.0 (CTCAE) at http://ctep.cancer.gov
		

7.2.2 Combination Therapy with Pembrolizumab

Attribution of Toxicity: When study interventions are administered in combination, attribution of an adverse event to a single component is likely to be difficult. Therefore, while the investigator may attribute a toxicity event to the combination, to lenvatinib alone or to pembrolizumab alone, for adverse events listed in the table in Section 7.2 above, both interventions must be held.

Restarting Study Interventions:

Participants may not have any dose modifications (no change in dose or schedule) of pembrolizumab in this study, as described in the table in Section 7.2 above. If pembrolizumab is to be held for a related toxicity, the dose will be skipped and restarted at the next cycle if resolved.

- If the toxicity does not resolve or the criteria for resuming treatment are not met, the participant must be discontinued from all study interventions, unless the toxicity can be clearly attributed to only one of the study therapies.
- If the toxicities do resolve and conditions are aligned with what is defined in the table in Section 7.2 above, the combination of lenvatinib and pembrolizumab may be restarted at the discretion of the investigator. In these cases where the toxicity is attributed to the combination or to lenvatinib alone, re-initiation of pembrolizumab as a monotherapy may be considered at the principal investigator's discretion.

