6.3.3 Rescue Medications and Supportive Care

Participants should receive appropriate supportive care measures as deemed necessary by the treating investigator. Suggested supportive care measures for the management of AEs with potential immunologic etiology are outlined along with the dose modification guidelines in Section 7.0. Where appropriate, these guidelines include the use of oral or IV treatment with corticosteroids, as well as additional anti-inflammatory agents if symptoms do not improve with administration of corticosteroids. Note that several courses of steroid tapering may be necessary as symptoms may worsen when the steroid dose is decreased. For each disorder, attempts should be made to rule out other causes such as metastatic disease or bacterial or viral infection, which might require additional supportive care. The treatment guidelines are intended to be applied when the Investigator determines the events to be related to pembrolizumab.

Note: If after the evaluation of the event, it is determined not to be related to pembrolizumab, the Investigator does not need to follow the treatment guidance. Refer to Section 7.0 for guidelines regarding dose modification and supportive care.

It may be necessary to perform conditional procedures such as bronchoscopy, endoscopy, or skin photography as part of evaluation of the event.

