7.0 DOSE DELAYS/DOSE MODIFICATIONS

Other holds and modifications beyond those described below may be made at the discretion of the PI. Dose holds or modifications for lenvatinib and pembrolizumab can occur independently of each other provided the toxicity is clearly attributable to the individual therapy, with the exception of toxicities that fall under the guidance in Section 7.2.

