7.1 Lenvatinib

Lenvatinib dose reduction and interruption for subjects who experience lenvatinib-related toxicity will be in accordance with the dose reduction instructions shown in the tables below. Any dose reduction below 4 mg/day must be discussed with the trial PI. Once the dose has been reduced, it cannot be increased at a later date.

Dose Reduction Recommendations for Lenvatinib Treatment-Related Toxicity

Initial Lenvatinib Dose	Adjusted Dose To Be Administered			
	Reduction 1	Reduction 2	Reduction 3	Reduction 4
20 mg QD	14 mg QD	10 mg QD	8 mg QD	4 ^a mg QD

a. Consult trial PI for further dose reduction recommendations.

Occurrence of Lenvatinib Treatment-related Toxicity^{a,b}	During Therapy		Adjusted Dose^f
	Grade 1, Tolerable Grade 2		
Any occurrence	Continue treatment		No change
Intolerable Grade 2^{c,d} and Grade 3^g			
First occurrence	Interrupt lenvatinib until resolved to tolerable Grade 2, or Grade 0-1		Reduce lenvatinib by 1 dose level

Second occurrence (same toxicity or new toxicity)	Interrupt lenvatinib until resolved to tolerable Grade 2, or Grade 0-1	Reduce lenvatinib by 1 more dose level
Third occurrence (same toxicity or new toxicity)	Interrupt lenvatinib until resolved to tolerable Grade 2, or Grade 0-1	Reduce lenvatinib by 1 more dose level
Fourth occurrence (same toxicity or new toxicity)	Interrupt lenvatinib until resolved to tolerable Grade 2, or Grade 0-1	Reduce lenvatinib by 1 more dose level
Grade 4^{e,g}		
Any occurrence	Discontinue lenvatinib	

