
a. An interruption of lenvatinib treatment for more than 21 days (due to lenvatinib treatment-related toxicities) will require a discussion with the Sponsor before treatment can be resumed.
 
b. Excluding alopecia. Initiate optimal medical management for nausea, vomiting, hypothyroidism, hypertension, and/or diarrhea prior to any lenvatinib interruption or dose reduction.
 
c. Applicable only to Grade 2 toxicities judged by subject and/or physician to be intolerable.
 
d. Obese subjects with weight loss do not need to return to the baseline weight or 10% of baseline weight (i.e. grade 1 weight loss). These subjects will restart the study drugs at a lower dose once their weight remains stable for at least 1 week and they reached the normal BMI (if the weight loss occurred but it is still above normal BMI, they can restart the study treatment at a lower dose once the weight has been stable for at least 1 week). Normal BMI should be used as the new baseline for further dose reductions.
 
e. Excluding laboratory abnormalities judged to be non-life-threatening, in which case manage as Grade 3.
 
f. Refer to table above for adjusted dose.
 
g. For asymptomatic Grade ≥ 3 elevations of amylase and lipase, the trial PI should be consulted to obtain permission to continue treatment.
		

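### The dual-hold rule in Section 7.2.2 has no grade or action limit, so read literally it contradicts the Continue rows for thyroid events in the Section 7.2 table

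*Combined protocol and SAP*

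**What the plan says.** Section 7.0 lets the two drugs be held or modified independently when a toxicity clearly belongs to one of them, "with the exception of toxicities that fall under the guidance in Section 7.2".

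Section 7.2.2 covers those exceptions. After noting that attribution is likely to be difficult with a combination, it says that whether the investigator attributes the event to both drugs together, "to lenvatinib alone or to pembrolizumab alone, for adverse events listed in the table in Section 7.2 above, both interventions must be held". Its first restart bullet takes the participant off all study interventions if the toxicity does not resolve or the resumption criteria are not met, unless the toxicity clearly belongs to one therapy only.

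The Section 7.2 table is organised by event, grade or condition, and action on pembrolizumab. Most rows withhold or discontinue. Two do not: hypothyroidism Grade 2 to 4 (continue, with thyroid hormone replacement) and hyperthyroidism Grade 2 (continue, with symptomatic treatment).

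For lenvatinib, the Section 7.1 table has a row for "Grade 1, Tolerable Grade 2" under which treatment continues unchanged. For intolerable Grade 2 and for Grade 3 the instruction is "Interrupt lenvatinib until resolved to tolerable Grade 2, or Grade 0-1". Footnote b adds: "Initiate optimal medical management for nausea, vomiting, hypothyroidism, hypertension, and/or diarrhea prior to any lenvatinib interruption or dose reduction". Section 7.1.3 sends liver events to the same table.

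**The concern.** A mandatory rule that refers to a table should agree with every row of it. Here the rule orders a hold for any event in the table, while two rows of that table order the opposite. A site that follows 7.2.2 to the letter would stop both drugs for hypothyroidism that the table says to treat through. Because of the restart bullet, that could become permanent discontinuation. A site that follows the table would carry on.

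At stake is consistent treatment of patients across the four intended sites, not the trial's inference. Dose received does feed into the per-protocol set (at least 80% of the targeted dosage, Section 15.5), but that set serves only sensitivity analyses.

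A lesser matter is that a reader who opens only the 7.1 table finds no reminder there that 7.2.2 overrides it for some Grade 2 events.

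**Working it through.** No figure in the plan depends on this point, so the check is a comparison of the texts.

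| Event and grade | 7.2 table, pembrolizumab | 7.2.2 read literally | 7.1 table, lenvatinib |
|---|---|---|---|
| Hypothyroidism, Grade 2 to 4 | Continue | Hold both | Medical management before any interruption (footnote b) |
| Hyperthyroidism, Grade 2 | Continue | Hold both | Continue if tolerable |
| Hyperthyroidism, Grade 3 or 4 | Withhold or discontinue | Hold both | Interrupt (Grade 3) or discontinue (Grade 4) |
| Diarrhea/colitis, Grade 2 | Withhold | Hold both | Continue if tolerable |
| AST/ALT or bilirubin elevation, Grade 2 | Withhold | Hold both | Continue if tolerable |

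**Step 1: the clash inside 7.2.** In the first two lines the table and 7.2.2 disagree. Limiting 7.2.2 to listed grades does not help, because these grades are listed. Count: hypothyroidism, 3 grade levels, plus hyperthyroidism, 1 grade level, gives 4 grade levels in 2 rows.

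**Step 2: whether another section cures it.** The exception in 7.0 places 7.2 above independent dosing under 7.1. It cannot rank one part of 7.2 against another. The introduction to 7.2 says pembrolizumab is withheld in accordance with the table, which points to the intended meaning, but 7.2.2 does not repeat that limit.

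**Step 3: the consequence under the restart bullet.** General instruction 2 of the table allows pembrolizumab to resume once the event is at Grade 0 or 1 and corticosteroid has been tapered. Suppose hypothyroidism stays at Grade 2 on replacement therapy. Under the literal hold it has not resolved, so all study treatment ends unless the event clearly belongs to one drug. That escape is narrow: footnote b of 7.1 treats hypothyroidism as a lenvatinib toxicity, the 7.2 table treats it as an immune-related one, and 7.2.2 itself says attribution is likely to be difficult.

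**Step 4: 7.1 against 7.2.2.** In the last two lines 7.1 and 7.2.2 differ, but 7.0 decides in favour of 7.2.2. The difference runs through the tolerable Grade 2 row and the restart level (tolerable Grade 2 in 7.1, against Grade 0 or 1 in 7.2). At Grade 3 the 7.1 table also interrupts lenvatinib. At Grade 4 it discontinues, or manages as Grade 3 if the event is a laboratory abnormality judged not life-threatening. Restart of the combination is already governed by 7.2.2.

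**Step 5: scale.** Section 2.5 reports hypothyroidism in 67% of a 30-patient study of this regimen, without grade or attribution. Applied to the planned 34 patients, 34 × 0.67 = 22.8. If between 25% and 100% of these events were Grade 2 or higher (an assumption, since the documents give no share), the range is 34 × 0.67 × 0.25 = 5.7 to 22.8, or about 6 to 23. This counts patients who might reach the row, not patients who would be wrongly held. It shows only that the event is common.

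**The case against.** The best defence is that nobody would read 7.2.2 that way. It refers to a table built on grade and action, and holding drugs where the table says to continue would make those rows pointless. Footnote b agrees with the table on hypothyroidism by putting medical management first. This is a fair account of the probable intent and keeps the point minor. It does not remove it: 7.2.2 is worded as an obligation, contains no limit, and carries a discontinuation rule.

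Three stronger readings are tempting and are not supported.

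- *A reader might infer that 7.1 and 7.2.2 contradict each other outright on Grade 2 diarrhea or liver enzymes.* They do not, because 7.0 stands directly above 7.1 and gives 7.2 precedence. What is missing is a cross-reference. Section 7.1.3 ("If signs occur indicating a decrease in liver function by 1 grade or more from baseline, the instructions contained in the table above") adds no separate conflict, since it only leads to the 7.1 table.
- *A reader might infer that 6.3.3 releases lenvatinib-attributed events from the dual hold.* It does say "The treatment guidelines are intended to be applied when the Investigator determines the events to be related to pembrolizumab" and that if "it is determined not to be related to pembrolizumab, the Investigator does not need to follow the treatment guidance". But 6.3.3 is a supportive-care section, and its next sentence sends dose modification back to Section 7.0. The note under the 7.2 table on events that are not immune-related is general, whereas 7.2.2 is specific and names lenvatinib-only attribution.
- *A reader might infer that the absence of a grade limit means holding both drugs for every Grade 1 event.* The table lists few Grade 1 events (myocarditis is one), so a fair reading stops at the listed grades. The problem is then confined to the thyroid Continue rows.

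**Conclusion.** The point holds in a narrow form and is minor. The wording of 7.2.2 contradicts two rows of the table it relies on, and nothing elsewhere resolves this. The discontinuation consequence rests on three conditions: a literal reading of 7.2.2, a thyroid event that does not resolve, and no clear attribution to one drug. The number of patients affected cannot be sized from the documents. The difference between 7.1 and 7.2.2 is already ranked by 7.0 and calls for no more than a cross-reference. No efficacy figure, sample size or decision rule is touched.

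**What to change.** **Main change, one clause in 7.2.2.** Reword the rule to say: for adverse events at a grade or condition for which the Section 7.2 table directs withhold or discontinue, both interventions must be held. The word *condition* is needed because new-onset type 1 diabetes and suspected SJS, TEN or DRESS are withheld without reference to a grade. Tying the rule to the table's action, not to a Grade 2 cut-off, also keeps Grade 1 myocarditis as a hold.

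**Secondary clarification, one footnote to the 7.1 toxicity table.** State that events at a grade or condition for which the 7.2 table directs withhold or discontinue (for example Grade 2 diarrhea/colitis and Grade 2 AST/ALT or bilirubin elevation) follow 7.2.2, including its restart conditions, and not the row that continues treatment for tolerable Grade 2. Because 7.1.3 uses the same table, it needs no edit of its own.

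**Optional.** A sentence in 6.3.3 and in the note on events that are not immune-related, saying that neither lifts the dual hold.

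The cost is a short wording amendment, with no change to design, sample size or analysis.
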